1. SYNOPSIS

Title	A Lead-in Study Evaluating Efficacy of GuessWhat Mobile App Therapy for Children With Autism
Design	Randomized, Investigator-Blinded,
Objectives	Determine whether GuessWhat Dtx can improve socialization in children with ASD after 4 weeks of use.
Endpoints	Primary: Change from week 0 to week 4 in the Vineland Adaptive Behavior Scales-3 Socialization Subscale, Comprehensive Parent Report Secondary: Change from week 0 to week 4 in Parent Stress Scale, and Child Emotion Recognition Score Exploratory/Descriptive: Descriptive analysis of child/parent surveys, treatment regimen compliance, demographics, missing data, and any resulting treatment related AEs
Study Sites	Participants will recruited by Stanford via remote online recruitment.
Planned Enrollment	A minimum of 500 to a maximum of 2,000 participants will be enrolled to achieve a minimum of 360 to a maximum 900 completed participants (n=180 - 450 in each of 2 arms) evaluable
Study Population	Autistic children 3-12 years old.
Subject Entry Criteria	Inclusion Criteria (1) Parent who is at least 18 years old of child with autism. (2) Child with autism is between 3 and 12 years old at time of baseline data collection. Exclusion Criteria (1) Parent does not have an Android or iOS smartphone compatible with GuessWhat App. (2) The parent is unable to speak/read in available translations of the study app: English, Spanish, Brazilian Portuguese.
Randomization	Block randomization stratified by child sex.
Treatment Regimen (Standard dose)	App is used 3 times a week for 15 minutes for 4 weeks

Duration of Study Participation	8 weeks
Statistical Methods	Independent Samples T-Tests
Study Measurements: Efficacy, Safety	Efficacy: Change in Vineland Adaptive Behavior Scales-3 Socialization Subscale week 0 to week 4 Safety: Adverse event reporting

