9.3 Safety Assessments

Adverse Events

Definition of an Adverse Event

The FDA Safety Guidance, referencing 21CFR312.32(a), defines an Adverse Event as follows:

Adverse event means any untoward medical occurrence associated with the use of a drug in humans, whether or not considered drug related.

An adverse event (also referred to as an adverse experience) can be any unfavorable and unintended sign (e.g., an abnormal laboratory finding), symptom, or disease temporally associated with the use of a drug and does not imply any judgment about causality. An adverse event can arise with any use of the drug (e.g., off-label use, use in combination with another drug) and with any route of administration, formulation, or dose, including an overdose.

Evaluating and Reporting of Adverse Events

All AEs will be promptly documented on the Adverse Event in RedCap and assessed by the Principal Investigator. Details of the event must include the dates of onset and resolution, severity, relationship to study drug, seriousness, and whether the event caused the subject to withdraw from the study, outcome and timing with regard to administration of the study drug.

Severity: Severity should be graded and recorded as follows:

- Mild: Awareness of event but easily tolerated
- Moderate: Discomfort enough to cause interference with usual activity

- **Severe:** Inability to carry out usual activity, incapacitating, requires medical intervention

Relationship: The relationship of the Adverse Event to the study device will be determined initially by the Investigator, and assessed using the following definitions:

- **Related:** There is a distinct temporal relationship between the event onset and administration of the study drug. There is a known reaction to agent or chemical group or predicted by known pharmacology. The event cannot be explained by subject's clinical state or other factors.
- **Unrelated:** Evidence exists that the AE has an etiology other than the study drug (e.g., pre-existing condition, underlying disease, intercurrent illness, or concomitant medication).

Final determination of relatedness will be made by the Stanford Institutional Review Board during an unanticipated problem or adverse event submission.

Expectedness: Whether or not the event was expected or unexpected. Further details on this can be found in section 8.5.

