These criteria, in addition to good clinical judgment, should be used as a guide for determining the causal assessment. If it is felt that the event is not related to study therapy, then an alternative explanation should be provided.

Serious Adverse Events (SAEs)

Suspected Unexpected Serious Adverse Reactions (SUSARs)

A SUSAR carries specific and time-based reporting requirements for the Sponsor of a clinical trial. Thus, after a Site Investigator reports an SAE, the FDA expects the Sponsor will determine whether it meets the definition of a SUSAR.

A SUSAR is defined according to 3 criteria:

1. The AE is deemed a “suspected adverse reaction” if there is a reasonable possibility that the study drug caused the AE. A “reasonable possibility” means there is evidence to suggest a causal relationship between the drug and adverse event.
2. The AE is “Serious” if it meets the definition of an SAE.
3. The AE is deemed “unexpected” if it is not listed in the Investigator’s Brochure (IB) or if in the IB, has not been reported at the severity observed.

In cases where the Investigator deems a SUSAR has occurred, it must file an IND Safety Report with the FDA. FPHU will require the assistance and cooperation of the Investigator and staff to provide accurate and complete information on the subject and observed SAE so that reporting requirements to the FDA can be met.

Reporting SUSARs to the FDA: IND Safety Reports

IND safety reports are used to submit reports of SUSARs to the FDA. There are 2 types of reports:

- A “15-day report” is used when the reported SAE is a SUSAR and requires that as much information as is available to the investigator and the sponsor, be submitted to the FDA in on the appropriate form. For US trials, the appropriate form is the FDA Form 3500A also commonly known as a “MedWatch” form.
- A “7-day report” is used when the SUSAR is considered to be fatal or life-threatening.

The 7-day and 15-day timelines begin the day that the Sponsor determines the information qualifies for reporting and are counted in calendar days – not business days. Therefore, it is important that the Site investigator carefully follow the reporting requirements.

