10.4 Analysis Populations

The following analysis populations will be defined for the study:

- (1) The intent-to-treat (ITT) population will include all randomized patients. Patients will be analyzed according to their assigned treatment arm. All efficacy analyses will be completed in the ITT population.
- (2) Per-Protocol (Treatment Compliant): This population is defined as any participant that began the initial 4-week treatment or control phase, completed both the pre and post assessments, and met a minimum compliance level of 50%. Participants that received incorrect intervention after randomization will be excluded from this population.
- (3) The safety population will include all patients who receive study treatment. Patients will be analyzed according to actual treatment received. All safety analyses will be completed in the safety population.

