A CONSORT diagram displaying the number of patients screened, eligible, and consented along with reasons for ineligibility will be provided. Graphical tools such as histograms, boxplots, and scatterplots will be created to assess quality of data and to display patterns over time.

Safety Analysis

Treatment related adverse events for GuessWhat intervention will be presented. Any adverse events occurring during any phase of the study judged by clinical sites' Primary Investigator (PI) to be related to the intervention will be recorded and presented in a table listing. The Safety population (see [analysis population details](#)) will be used for this analysis that will include randomized participants. The severity of each event will be evaluated by the PI and presented with the recorded events. If there are frequently occurring treatment related adverse events,

a frequency table will be included, to rank events from most frequent to most rare. Subjects will be included in the actual treatment group received.

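### The planned safety output shows only app-related adverse events, so it allows no comparison of all adverse events between arms, and it is unclear whether controls are in the safety population

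*Combined protocol and SAP*

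**What the plan says.** **Output.** Under Safety Analysis in section 10.5, AEs judged by the PI "to be related to the intervention will be recorded and presented in a table listing", with severity. A ranked frequency table is conditional: "If there are frequently occurring treatment related adverse events". The synopsis (section 1) gives the descriptive endpoint as "any resulting treatment related AEs".

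**Collection.** Section 9.3 is wider. It defines an AE without regard to cause and states: "All AEs will be promptly documented on the Adverse Event in RedCap and assessed by the Principal Investigator". Severity, seriousness and relationship are to be recorded for each event. Section 8.1 (Week 4 Post-Test 1) asks Treatment and Control alike about safety events.

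**Population.** Section 10.4 states: "The safety population will include all patients who receive study treatment". Section 10.5 says that this population "will be used for this analysis that will include randomized participants", grouped by the treatment actually received.

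**Objective.** Section 5.2 lists the safety of the device in home use as a secondary objective.

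**Broader statements.** Section 7.2 (Treatment Precautions) says that all AE information will be included once the trial is complete. The synopsis lists adverse event reporting as the safety measurement, with no relatedness limit. Neither names a table, a denominator or a comparison.

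**The concern.** The trial collects AEs regardless of cause and has a concurrent randomized control arm that is asked about them. The planned output then drops every event not judged related to the app. A control child who is not using the app can hardly have an event judged related to it, so splitting the listing by arm would still give no comparison.

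A short listing could mean that the app is safe, or that few events were attributed to it. A reader of the report could not tell these apart. A table of all AEs by arm does not rest on attribution. The population wording adds a second problem: two statisticians working from sections 10.4 and 10.5 could build different safety populations, one with controls and one without. What is at stake is the answer to the secondary safety objective, not any efficacy result.

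**Working it through.** The documents state no AE rate and no safety sample-size figure, so there is no figure of the plan to reproduce. The main check is textual.

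**1. Collected against reported.**

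| Item | Collected | Planned output |
|---|---|---|
| AEs judged related | yes (9.3) | listing; frequency table if frequent (10.5) |
| AEs judged unrelated | yes (9.3) | none specified |
| SAEs, any cause | yes (9.3) | no summary; expedited regulatory reporting only (9.3) |
| AEs in controls at week 4 | asked (8.1) | only if judged related to the app |

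**2. Who applies the filter.** Section 10.5 names the PI. Section 9.3 gives the first judgment to the investigator and the final one to the institutional review board. Either way, what reaches the listing depends on attribution.

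**3. Are controls in the safety population?** Section 10.4 takes those who receive study treatment. Control is treatment as usual (7.2), and controls are told that they will wait before starting the app (8.1). Read literally, section 10.4 leaves them out, at least until they start. Section 10.5 refers to randomized participants and to treatment groups, which suggests that they are in. No section says whether treatment as usual counts as study treatment.

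**4. What an all-AE table could show.** This measures the precision of the remedy, not the size of the defect. Inputs: 180 to 450 completers per arm (section 1); the AE proportion p, taken as equal in both arms, is assumed. The 95% half-width of the risk difference is 1.96 × √(2p(1−p)/n). For p = 0.05 and n = 180: 1.96 × √(2 × 0.05 × 0.95/180) = 0.045, or 4.5 points.

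| Assumed p | n = 180 per arm | n = 450 per arm |
|---|---|---|
| 2% | ±2.9 | ±1.8 |
| 5% | ±4.5 | ±2.8 |
| 10% | ±6.2 | ±3.9 |
| 20% | ±8.3 | ±5.2 |

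Newcombe's method for 9/180 against 9/180 gives ±4.8 points, close to the ±4.5 above.

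**5. Why the denominator must be stated.** Suppose that 9 of 180 week-4 responders in an arm report an AE (assumed): 9/180 = 5.0%. Section 10.2 expects 36% of enrolled families to complete all procedures, so 360/0.36 = 1,000 enrolled, or 500 per arm, and 9/500 = 1.8%. At the synopsis minimum of 500 enrolled, or 250 per arm, 9/250 = 3.6%. This treats enrolled as randomized and completers as week-4 responders. Completing all procedures is not the same as answering the week-4 question. The synopsis also implies higher completion: 360/500 = 72% or 900/2,000 = 45%.

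**The case against.** The strongest reply is that section 5.2 sets no comparison for safety, whereas the primary objective in section 5.1 does name the waitlist control. A listing of related events with severity is a recognizable descriptive answer for a game that section 7.2 rates at everyday risk, with no AEs reported in testing. Sections 1 and 7.2 also contain unfiltered statements about AEs, and since all AEs are documented, the table could still be made later.

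Part of this stands. A formal comparative safety aim would go beyond the protocol, so the table should be descriptive. But the unfiltered statements specify no analysis, and section 10.5, which does specify one, filters. That the data will exist is a reason to plan the table now, because it costs almost nothing.

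The population wording can be defended too: treated participants are a subset of those randomized, and section 10.5 points back to section 10.4. That reading is possible, but it does not say where controls belong.

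A reader might infer more than the documents support:

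- *That unrelated AEs will not be recorded, because section 10.5 speaks of recording related ones.* Section 9.3 requires all AEs to be documented.
- *That controls are definitely excluded from safety analysis.* The text is ambiguous, not decisive.
- *That the drug wording of the relatedness definition, such as "There is a known reaction to agent or chemical group or predicted by known pharmacology", would bar any event from being called related to a phone game.* Section 9.3 also says "These criteria, in addition to good clinical judgment, should be used as a guide for determining the causal assessment", and it asks for an alternative explanation when an event is felt to be unrelated.
- *That safety events are not scheduled, because section 13 shows no AE row.* The row for the change in treatment and play questionnaire may be the same check-in, or a row may have been lost when the table was extracted.

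The last two are side notes on wording and layout and form no part of this point.

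**Conclusion.** The point holds as a cheap improvement. Followed as written, section 10.5 yields a listing that depends on attribution and gives no usable comparison with the control arm, and sections 10.4 and 10.5 do not settle whether controls are in the safety population. This is a stated reporting rule with a better alternative at almost no cost, not merely a missing detail.

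The effect of the filter cannot be quantified from the documents. The half-widths in the working rest on assumed AE proportions and show only that the added table would be imprecise for small differences. No efficacy conclusion, sample size or primary analysis is affected. The documents give no ground for inferring that the app is unsafe or that events would be concealed.

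**What to change.** 1. In the Safety Analysis of section 10.5, add a descriptive table of all AEs and all SAEs by randomized arm for the first 4 weeks, regardless of relatedness: number, percentage, and risk difference with 95% confidence interval. Keep related AEs as a subset. Give percentages on two denominators: participants randomized, and participants who answered the week-4 safety question. Summarize AEs during any later app use by controls separately.
2. Reconcile sections 10.4 and 10.5 so that the population used for this table explicitly covers both randomized arms.

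**Cost.** One extra table and a wording change. Section 8.1 already asks both arms the question, so no new data collection is needed.

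**Downside.** The comparison is imprecise for small differences and open to reporting bias. Parents know their arm, treatment families get more contact (activity follow-up in section 7.2, weekly reminders in section 8.1), and many participants may not respond at week 4. It should be labelled descriptive, with no test and no claim of equivalence.

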11. RECORDING AND COLLECTION OF DATA

11.1 Case Report Form

The Investigator or designee will record all data collected on the electronic Case Report Form (eCRF) provided for that purpose. For this study, REDCAP will be the eCRF. The site will be suitably trained on the use of the eCRF and appropriate site personnel will be provided electronic signatures.

All site entries will be made in a secured web site and the Principal Investigator will review the record for completeness. Upon completion of the review, the PI will sign electronically in the signature page of the eCRF.

The Investigator or designee will make necessary eCRF corrections. The investigator must authorize the corrections to the entered data on eCRF.

Specific instructions on use of the EDC system and guidelines for data entry and correction will be provided to the sites.

11.2 Study Files and Subject Source Documents

Subject confidentiality is strictly held in trust by the participating investigators, research staff, the Sponsor and their designees. This confidentiality is extended to cover testing of biological samples in addition to the clinical information relating to subjects. Authorized representatives of the Sponsor may inspect all documents and records required to be maintained by the Investigator, including but not limited to, medical records (office, clinic or hospital) and pharmacy records for the subjects in this study. Any data, specimens, forms, reports, and other records that leave the site will be identified only by a subject identification number to maintain confidentiality.

The Investigator must maintain adequate and accurate records to enable the conduct of the study to be fully documented and the study data to be subsequently verified. These documents include Investigators' Study Files and original subject clinical source documents generated at the study site. The term "original" means the first recording of the data.

The Investigator will ensure the site master files are maintained, including the study protocol and its amendments, IRB and regulatory approvals with associated correspondence, informed consents, study drug records, staff curriculum vitae, all correspondence, and other appropriate documents.

Subject clinical source documents may include, but are not limited to, subject hospital/clinic records. The Investigator must assure that all original source documents are available to support monitoring activities.

11.3 Monitoring

Monitoring will be conducted according to the applicable ICH and GCP guidelines to ensure protocol adherence, quality of data, drug accountability, compliance with regulatory requirements and continued adequacy of the investigational site and its facilities. The site study staff will cooperate in the monitoring process by ensuring the availability of the eCRFs, source documents and other necessary documents at the time of monitoring and by prompt attention to any matters brought to their attention by the monitor.

11.4 Audit

ICH guidelines for GCP require independent inspection of clinical program activities. Such inspections may be performed at any time - before, during and/or after the study. The site Investigator and site study staff are

responsible for maintaining the site master file containing all study-related regulatory documentation as outlined by the Sponsor that will be suitable for inspection at any time by the Sponsor, its designees, and/or regulatory agencies. The Investigator understands and agrees to give access to the necessary documentation and files.

11.5 Retention of Data

The site PI will maintain the records of device/tablet disposition, final eCRFs, worksheets, and all other study-specific documentation (e.g., study file notebooks or source documentation) until notified by the sponsor that records may be destroyed. To avoid error, the investigator will contact the sponsor or their designated representative before the destruction of any records pertaining to the study to ensure they no longer need to be retained. In addition, the sponsor will be contacted if the site PI plans to leave the institution so that arrangements can be made for the transfer of records.

12. ETHICS

12.1 Ethics Committee

A properly constituted, valid IRB/IEC must review the treatment plan and procedures, the Investigator's informed consent document, and related subject information. It is the responsibility of the Investigator to ensure that all aspects of institutional review are conducted in accordance with current regulations governing the jurisdiction where the study is conducted. The Sponsor (or designee) must receive a letter documenting IRB/IEC approval that specifically identifies the title of the treatment plan, subject information sheet, and ICF.

12.2 Subject Information and Consent

It is the responsibility of the site Investigator to ensure that written informed consent is obtained from the subject or legal representative before any activity or procedure is undertaken that is not part of routine care. The informed consent must comply with local regulations.

The background of the study, the procedures, the potential benefits and risks of the treatment, and the fact that treatment is voluntary for the subject must be explained to the subject or legal representative. The subject or representative must be given sufficient time to consider whether to receive compassionate treatment. A copy of the ICF, signed and dated by the subject/representative and the site Investigator (or designee), must be given to the subject/representative.

Each consent form should contain an authorization allowing the Investigator and the Sponsor (or designee) to use and disclose protected health information (PHI) (i.e., subject-identifiable health information) in compliance with local law.

13. SCHEDULE OF ASSESSMENTS

	Screening Week 0	Enrollment Week 1	Primary Assessment Week 4	Check-In 2 Week 12
Screening				
Pre-Screening Consent	X			
Screening Questionnaire	X			
Informed Consent	X			

Assessments				
Demographics Questionnaire	X			
Mobile Autism Risk Assessment	X			
Parent Stress Scale	X		X	X
Vineland Adaptive Behavior Scales-3 Socialization Subscale Parent Report	X		X	X
Child Emotion Task	X		X	X
App Download	X		X	
Change in treatment/play questionnaire			X	X
Allocation/Randomization		X
